## **8.4 Reporting Procedures – Notifying the IRB**

### **8.4.1 Adverse Event Reporting**

At each contact with the subject, the investigator must seek information on adverse events by specific questioning and, as appropriate, by examination. Information on all adverse events should be recorded immediately in the source document, and also in the appropriate adverse event module of the case report form (CRF). All clearly related signs, symptoms, and abnormal diagnostic procedures results should recorded in the source document, though should be grouped under one diagnosis.

The clinical course of each event should be followed until resolution, stabilization, or until it has been determined that the study treatment or participation is not the cause. Serious adverse events that are still ongoing at the end of the study period must be followed up to determine the final outcome.

Any serious adverse event that occurs after the study period and is considered to be possibly related to the study treatment or study participation should be recorded and reported immediately.

The Common Terminology Criteria for Adverse Events, Version 5.0, will be used for assessing the severity of adverse events.

The following will be reported and monitored for IPS:

- Grade 1-Asymptomatic or mild symptoms; clinical or diagnostic observations only; intervention not indicated.
- Grade 2- Moderate; minimal, local or noninvasive intervention indicated; limiting age-appropriate instrumental ADL
- Grade 3- Severe or medically significant but not immediately life-threatening; hospitalization or prolongation of existing hospitalization indicated; limiting self care ADL
- Grade 4- Life-threatening consequences; urgent intervention indicated
- Grade 5- Death

### **8.4.2 Serious Adverse Events and Unanticipated Problems Reporting**

Investigators must conform to the adverse event reporting timelines, formats and requirements of the various entities to which they are responsible, but at a minimum, those events that must be reported are those that are:

- related to study participation,

CONFIDENTIAL

This material is the property of the NYU School of Medicine and Langone Medical Center. Do not disclose or use except as authorized in writing by the study sponsor

- unexpected, and
- serious or involve risks to subjects or others (see definitions, [section 8.1](#)).

Events should be reported using the NYU CTO Medical Events Form.

Adverse events that do not fit the above immediately reportable criteria must still be reported to the IRB at each annual review, either in a summary or tabular format.

Incidents or events that meet the OHRP criteria for UPs require the creation and completion of an UP report form. It is the site investigator's responsibility to report UPs to their IRB and to the overall principal investigator. The UP report will include the following information:

- Protocol identifying information: protocol title and number, PI's name, and the IRB project number;
- A detailed description of the event, incident, experience, or outcome;
- An explanation of the basis for determining that the event, incident, experience, or outcome represents an UP;
- A description of any changes to the protocol or other corrective actions that have been taken or are proposed in response to the UP.

To satisfy the requirement for prompt reporting, UPs will be reported using the following timeline:

- UPs that are SAEs will be reported to the IRB within 10 working days and to the DSMC/study sponsor/medical monitor within 24 hours of the site awareness for all deaths and immediately life-threatening events, whether related or unrelated of the investigator becoming aware of the event.
- Any other UP will be reported to the IRB and to the DSMC/study sponsor within 10 working days of the investigator becoming aware of the problem.
- All UPs should be reported to appropriate institutional officials (as required by an institution's written reporting procedures), the supporting agency head (or designee), and OHRP within 5 days of the IRB's receipt of the report of the problem from the investigator.

Serious adverse event reporting will begin in conjunction with the date of treatment administration. Any SAEs occurring prior to study drug administration that the investigator believes may have been caused by a protocol procedure must be reported immediately to the principal investigator, assigned medical monitor, with a notification email sent to [[contact]](mailto:[contact]) and recorded on the case report form.

All fatal or life-threatening adverse events must be immediately reported to the Principal Investigator, via appropriate reporting mechanism and the NYU Langone Health IRB by telephone or e-mail. Within 24 hours of the event, the Serious Adverse Event Form must be emailed to [[contact]](mailto:[contact]) whether full information regarding the event is known or not.

Additional follow-up by the investigator will be required if complete information is not known. De-identified source documentation of all examinations, diagnostic procedures, etc. which were completed with respect to the event should be included with the SAE form. For laboratory results, include the laboratory normal ranges.

All other serious adverse events must be reported to the principal investigator and DSMC's appointed medical monitor within 24 hours by e-mail ([[contact]](mailto:[contact])). The Serious Adverse Event Form must also be emailed to the principal investigator, assigned medical monitor and emailed to [[contact]](mailto:[contact]), this documentation will be forwarded to the appropriate additional personnel within 24 hours of the event whether full information regarding the event is known or not. Additional follow-up by the investigator will be required if complete information is not known.

Current contact information shall be maintained at the site within the regulatory binder.

All serious adverse events (SAEs) will be evaluated by the DSMC if meeting the requirements for

#### CONFIDENTIAL

This material is the property of the NYU School of Medicine and Langone Medical Center. Do not disclose or use except as authorized in writing by the study sponsor

expedited reporting, the investigator is responsible for reporting all SAEs to the appropriate IRB, DSMC, and FDA.

#### Follow-up report:

As a follow-up to the initial report, the investigator shall provide further information, as applicable, on the unanticipated event or the unanticipated problem in the form of a written narrative. This should include a copy of the completed Unanticipated Problem form, and any other diagnostic information that will assist the understanding of the event.

#### Other Reportable events

- **Deviations from the study protocol**

Any protocol deviations that may affect the scientific soundness of the study, or affect the rights, safety, or welfare of study subjects, must be reported to the NYU's IRB as soon as a possible, but **no later than 10 working days** of the protocol deviation.

### 8.4.3 Reporting of Pregnancy

Should a pregnancy occur, it must be reported immediately to the principal investigator and DSMC appointed medical monitor [[contact]](mailto:[contact]) in accordance with the procedures described below. Pregnancy in itself is not regarded as an adverse event unless there is a suspicion that the investigational regimen may have interfered with the effectiveness of a contraceptive medication. This will be reported to the IRB if necessary.

### 8.5 Reporting Procedures- Notifying the IRB

Federal regulations require timely reporting by investigators to the NYULH IRB of unanticipated problems posing risks to subjects or others. The following describes the NYULMC IRB reporting requirements, though Investigators at participating sites are responsible for meeting the specific requirements of their IRB of record.

This section also specifies the NYULH IRB requirements for investigator reporting of unanticipated problems posing risk to subjects or others, including adverse events. The IRB requirements reflect the current guidance documents released by the Office of Human Research Protections (OHRP), and the Food and Drug Administration (FDA) and are respectively entitled "Guidance on Reviewing and Reporting Unanticipated Problems Involving Risks to Subjects or Others and Adverse Events" and "Guidance for Clinical Investigators, Sponsors, and IRBs: Adverse Event Reporting – improving Human Subject Protection".  
The NYU IRB address is:

NYU School of Medicine IRB  
[name]  
[name]

#### **Report Promptly, but no later than 10 working days:**

Researchers are required to submit reports of the following problems promptly but no later than 10 working days from the time the investigator becomes aware of the event:

- **Unanticipated problems including adverse events that are unexpected and related and harmful**
  - **Unexpected:** An event is "unexpected" when its specificity and severity are not accurately reflected in the protocol-related documents, such as the IRB-approved research protocol, any applicable investigator brochure, and the current IRB- approved informed consent document and other relevant sources of information, such as product labeling and package inserts.
  - **Related to the research procedures:** An event is related to the research procedures if in the opinion of the principal investigator or sponsor, the event was more likely than not to be caused by the research procedures.
  - **Harmful:** either caused harm to subjects or others, or placed them at increased risk

CONFIDENTIAL

This material is the property of the NYU School of Medicine and Langone Medical Center. Do not disclose or use except as authorized in writing by the study sponsor

### **Other Reportable events:**

The following events also require prompt reporting to the IRB, though **no later than 10 working days**:

- **Complaint of a research subject** when the complaint indicates unexpected risks or the complaint cannot be resolved by the research team.
- **Protocol deviations or violations** (includes intentional and accidental/unintentional deviations from the IRB approved protocol) for any of the following situations:
  - one or more participants were placed at increased risk of harm
  - the event has the potential to occur again
  - the deviation was necessary to protect a subject from immediate harm
- **Breach of confidentiality**
- **Incarceration of a participant** when the research was not previously approved under Subpart C and the investigator believes it is in the best interest of the subject to remain on the study.
- **New Information indicating a change to the risks or potential benefits** of the research, in terms of severity or frequency. (e.g. analysis indicates lower-than-expected response rate or a more severe or frequent side effect; Other research finds arm of study has no therapeutic value; FDA labeling change or withdrawal from market)

## **8.6 Reporting Procedures – Notifying the Study Sponsor (NYU Langone Health)**

The study clinician will complete a SAE Form within the following timelines:

- All deaths and immediately life-threatening events, whether related or unrelated, will be recorded on the SAE Form and submitted to the principal investigator, appointed medical monitor, as well as email notification to [[contact]](mailto:[contact]) within 24 hours of site awareness. See Section 1, Key Roles for contact information.

All SAEs will be followed until satisfactory resolution or until the site investigator deems the event to be chronic or the adherence to be stable. Other supporting documentation of the event may be requested by the DSMC/principal investigator and should be provided as soon as possible.

As a follow-up to the initial report, within the following 48 hours of awareness of the event, the investigator shall provide further information, as applicable, on the unanticipated event or the unanticipated problem in the form of a written narrative. This should include a copy of the completed Unanticipated Problem form, and any other diagnostic information that will assist the understanding of the event. Significant new information on ongoing unanticipated adverse effects shall be provided promptly to the study sponsor.

## **8.7 Reporting Procedures**

The reportable events noted above will be reported to the IRB using the form: “Reportable Event Form” or as a written report of the event (including a description of the event with information regarding its fulfillment of the above criteria, follow-up/resolution and need for revision to consent form and/or other study documentation).

Copies of each report and documentation of IRB notification and receipt will be kept in the Clinical Investigator’s study file.

The Principal Investigator is responsible for reporting all unexpected problems involving risk to participants or others to NYU Perlmutter Cancer Center CTO.

## **8.8 Safety Oversight**

### **CONFIDENTIAL**

This material is the property of the NYU School of Medicine and Langone Medical Center. Do not disclose or use except as authorized in writing by the study sponsor

Safety oversight will be under the direction of a DSMC composed of individuals with the appropriate expertise. The DSMC will meet at least annually to assess safety and efficacy data of the study. The DSMC will operate under the rules of an approved charter.

All Internal SAEs reported, occurring to subjects on clinical trials that are not monitored by any other institution or agency, are reported to the principal investigator, DSMC appointed medical monitor, and to the DSMC via email: [[contact]](mailto:[contact]) and reviewed within 48 hours by the medical monitor. Based on the review, one of three determinations will be made:

- SAE report is considered to be adequate
- Queries for clarification to PI regarding treatment attribution and/or resolution of SAE or completeness of other information. The committee may request a cumulative review of all SAEs on the study to date.
- Request for full DSMC committee review of protocol at the next scheduled meeting.

The DSMC Coordinator will record the committee's decision and incorporate it into the study summary for the next protocol review.

## 9 Clinical Monitoring

Clinical site monitoring is conducted to ensure that the rights and well-being of human subjects are protected, that the reported trial data are accurate, complete, and verifiable, and that the conduct of the trial is in compliance with the currently approved protocol/amendment(s), with GCP, and with applicable regulatory requirement(s).

It is the responsibility of the Principal Investigator to oversee the safety of the study at his/her site. This safety monitoring will include careful assessment and appropriate reporting of adverse events as noted above, as well as the construction and implementation of a site data and safety monitoring plan detailed below. Serious adverse events are evaluated regularly by the principal investigator in conjugation with the research team, the DSMC is notified of serious adverse events via email initially, reviewed offline by the designated medical monitor, and presented at the next DSMC monthly meeting. The DSMC will review the study at least annually. Medical monitoring will include a regular assessment of the number and type of serious adverse events.

### 9.1.1 Data Monitoring Committee

This investigator-initiated study will be monitored by the Data and Safety Monitoring Committee (DSMC) of the New York University (NYU) Perlmutter Cancer Center (PCC). The DSMC operates based on the 2017 National Cancer Institute approved Charter. It is an existing and multidisciplinary committee (consisting of clinical investigators/oncologists, biostatisticians, nurses, and research administration staff knowledgeable of research methodology and design and in proper conduct of clinical trials) that is responsible for monitoring safety, conduct and compliance in accordance with protocol data monitoring plans for interventional clinical trials conducted in the NYULH Perlmutter Cancer Center that are not monitored by another institution or agency. The DSMC reports to the Director of the NYULH PCC.

Per the NYU PCC Institutional Data and Safety Monitoring Plan, this pilot trial will be monitored by DSMC *annually* (from the date the first patient is enrolled), at protocol-specified interim time points, and at the completion of the study prior to study closure. This review includes accrual data, subject demographics and adverse events. The Principal Investigator is required to attend the review of their study. Additional reviews can be scheduled based on SAE reports, investigator identified issues, external information, etc. The DSMC will review safety data annually. DSMC summary reports are available to facilitate the review and monitoring of this study. These reports include the following: patient listings and summary reports that describe study enrollment and accrual, eligibility, demographic characteristics, dose modifications,

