Myeloablative regimens are associated with treatment-related or non-relapse-related mortality rates of approximately 20-30%. The most common toxicity of TBI based conditioning regimens is radiation-induced interstitial pneumonitis. When delivered as a single high-dose (8-10 Gy) fraction, TBI is associated with a 50% risk of radiation-induced interstitial pneumonitis with a 50% fatality rate. Even with fractionation, pneumonitis can occur in up to 25% of patients though the risk of fatal events is reduced. The reported incidence of non-infectious pneumonitis or idiopathic pneumonia syndrome (IPS) after TBI-based myeloablative conditioning regimens range from 7% to 35%. In a recently published single institution series with 202 patients in which 13.2 Gy TBI was delivered with opposed lateral beams, IPS occurred in 21% of patients at a median of 16 days with a mortality rate of 45%. Those undergoing TBI with a high-dose rate (HDR) had a nearly 3-fold increase in IPS (29%) compared with those receiving low-dose rate (LDR) TBI

CONFIDENTIAL

This material is the property of the NYU School of Medicine and Langone Medical Center. Do not disclose or use except as authorized in writing by the study sponsor

(10%). Lung shielding was not used. Other factors, aside from dose rate, associated with IPS on multi-variate analysis were use of lower energy, a higher comorbidity index, and the specific conditioning regimen used. Another single institution series reviewed 77 patients receiving once-daily TBI between years 2000 and 2016. In this study, the cumulative rate of pulmonary toxicity was assessed. Dose rate, total dose and conditioning regimen were significant factors for the development of pulmonary toxicity. It is important to note that the definition of HDR versus LDR is not standardized for different studies and while Gao et al., defined the HDR vs. LDR dose rate cut-off at 15 cGy/min, Kim et al., defined the dose rate cut-off at 6 cGy/min.

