#### CONFIDENTIAL

This material is the property of the NYU School of Medicine and Langone Medical Center. Do not disclose or use except as authorized in writing by the study sponsor

abnormalities, and secondary malignancy. These risks, especially secondary malignancy, are potentially higher for adolescents and young adults. This study introduces the added element of linac based VMAT TBI.

One potential risk of linac based VMAT TBI is that a higher dose rate will be used for treatment delivery as compared with conventional methods of delivering TBI and this could potentially result in higher rates of idiopathic pneumonia syndrome.

Another potential risk of linac based VMAT TBI is that the lower dose to the lungs and kidneys could result in an increased risk of relapse. It should be noted, however, that most conventional methods for TBI block dose to the lung using lung blocks or other methods so in that sense, the use of VMAT to limit dose the lung is not unique. Furthermore, there is some preliminary data on total marrow irradiation (TMI) in which organs such as the lungs and kidneys are intentionally spared completely and the preliminary outcomes show the validity of this approach.

There could be other risks associated with a novel-treatment approach including the risks for possible errors in treatment delivery. As detailed below, many measures are taken to ensure accurate and precise dose delivery to minimize the risk of any errors.

There could be other unknown or unanticipated risks with regard to toxicity and efficacy of linac based VMAT TBI that are not present with conventional methods of TBI delivery.

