### **5.5 Study Duration**

The study will continue until 1 year after the day of transplant for last subject enrolled. The primary endpoint is up to 100 days post-transplant and the secondary endpoint is up to 1 year post-transplant. Accrual estimated over 15 months.

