### **5.6 Total Number of Participants**

35 participants will be accrued for this study. Consenting, screening, and treatment visits will take place at NYU Langone Health PCC.

Recruitment will end when 35 participants are accrued. It is expected that fewer than 10% of patients or prospective subjects will not be evaluable for dosimetric evaluation. Up to 70 participants may sign consent in order to achieve 35 accrued subjects; this is to account for screen failures.

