## 10 Statistical Considerations

The study is designed to estimate the proportion of patients who achieve excellent coverage while sparing the lung as quantified by meeting the following dosimetric parameters: (all parameters must be met).

1. V100%= >90% (90% of PTV volume getting 100% of the dose).
2. D98>85% (98% of the volume getting at least 85% of the dose).
3. Mean Lung dose <900cGy.

The key secondary objective is to estimate the cumulative incidence of non-infectious idiopathic pneumonia syndrome (IPS) within the first 100 days post transplant.

Non-infectious pneumonia syndrome is defined by the American Thoracic Society as at least 1 of the following (i, ii, iii) without concurrent infection detected on blood culture, bronchoalveolar lavage, lung biopsy or sputum.

- i. Multilobar infiltrates on chest radiograph or computed tomography (CT)
  - ii. Symptoms and signs of pneumonia including dyspnea, cough, cyanosis, hypoxia or pyrexia
  - iii. New or increased restrictive patterns on pulmonary function testing or increased alveolar to arterial oxygen difference
- There must be no concurrent cardiac dysfunction, acute renal failure, or iatrogenic fluid overload as etiology for pulmonary dysfunction.

Additional secondary objectives include:

Time to the first occurrence of acute GVHD, transplant related mortality or death in the first 100 days will be estimated.

Event Free Survival (EFS): interval from date of transplant to date of first objective disease progression or relapse or death from any cause. Patients without these failures will be censored at the last date that they were assessed and evaluated as failure free.

Additional Dosimetric parameters of the linac based VMAT TBI plan not included in the primary endpoint:

- Mean dose to each kidney (Dmean) < 11Gy.
- Maximum dose to 2cc of the entire body (D2cc) <130% of Rx dose.
- Maximum dose to 0.03cc of OARs < 120% of Rx dose.

Patient-specific quality assurance (PSQA) for each treatment plan:

- A pass rate of higher than 90% of points using a gamma criterion 5% at 3 mm and a dose threshold of 10% is required between the delivered dose to an array of detectors and the planned dose for each individual VMAT field.

Exploratory endpoints are:

- Dosimetric consequences on the PTV, lungs and kidneys as a result of patient setup variations
- in vivo transit dosimetry using SNC PerFraction (Fraction N) for dose tracking and correlation with patient setup

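### DSMC review is promised at interim time points that the protocol never names, and no cumulative IPS count triggers study-level review of the key secondary safety endpoint.

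*Combined protocol and SAP*

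**What the plan says.** Section 9.1.1 sets the DSMC schedule: annually, counted from first enrolment, "at protocol-specified interim time points, and at the completion of the study prior to study closure". Section 8.8 gives the frequency as a minimum: "The DSMC will meet at least annually to assess safety and efficacy data of the study". On size and pace, section 5.6 says "35 participants will be accrued for this study" and section 5.5 says "Accrual estimated over 15 months".

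On the hazard, section 2.4.1 opens its technique-specific risks with the higher dose rate of VMAT delivery and says "this could potentially result in higher rates of idiopathic pneumonia syndrome". Section 10 adds: "The key secondary objective is to estimate the cumulative incidence of non-infectious idiopathic pneumonia syndrome (IPS) within the first 100 days post transplant". Section 2.1 supplies reference figures: 7% to 35% across published series and, in one 202-patient series, 21% overall, 10% at low and 29% at high dose rate, with onset at a median of 16 days.

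Sections 10 and 10.1 contain no interim look and no IPS threshold, and they treat secondary analyses as mainly descriptive. Section 5.8 lists unacceptable risk as a reason to suspend, without a number.

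**The concern.** Section 9.1.1 points to content that does not exist in the protocol. A DSMC following the plan literally has one fixed obligation before accrual ends: the annual review.

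This matters for IPS because it is a known complication of TBI-based conditioning. Any single case is unsurprising, so reviewing cases one at a time cannot readily tell a 10% rate from a 29% rate. That takes a cumulative count set against a reference rate. The protocol cites the rates but attaches no action to them. If the technique did raise IPS, most subjects could be enrolled before the plan requires anyone to compare the total with a benchmark.

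**Working it through.** The plan gives no IPS design figure to reproduce. Its only design calculation concerns the dosimetric primary endpoint.

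**Inputs.** N = 35 (5.6); accrual 15 months (5.5); annual review counted from first enrolment (9.1.1); IPS rates 7%, 10%, 21%, 29% and 35% (2.1). Assumptions: uniform accrual, review at exactly month 12, and 0 to 1 month from enrolment to transplant.

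**Enrolled at the first mandatory review.** Rate = 35/15 = 2.33 per month; 35 × 12/15 = 28, or 80%. If accrual took 24 months: 35 × 12/24 = 17.5.

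**With 100 days of follow-up at month 12.** 100 days = 100/30.44 = 3.29 months. No lag: (12 − 3.29) × 2.33 = 20.3. One-month lag: (12 − 3.29 − 1) × 2.33 = 18.0.

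**Expected IPS cases among 28 (28 × rate).**

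| True rate | 7% | 10% | 21% | 29% | 35% |
|---|---|---|---|---|---|
| Cases | 2.0 | 2.8 | 5.9 | 8.1 | 9.8 |

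These are upper figures, because 8 to 10 of the 28 have not finished the 100-day window. The 16-day median onset suggests that most of their cases would already have occurred.

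**What an explicit rule could do.** Example: prior Beta(0.2, 1.8), whose mean is 0.2/2 = 10%. After x cases in n treated subjects the posterior is Beta(0.2 + x, 1.8 + n − x). Review is triggered when P(rate > 10%) exceeds 0.97, checked at n = 5, 10, 15, 20, 25 and 30. The smallest triggering counts are 3, 4, 5, 6, 7 and 7. At n = 25, 6 cases give 0.968, so that bound only just excludes 6.

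Exact binomial recursion over the six looks, with accrual held at the trigger and 35 enrolled otherwise:

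| True rate | P(trigger) by n = 25 | P(trigger) by n = 30 | Expected enrolment |
|---|---|---|---|
| 10% | 3% | 4% | 34.2 |
| 21% | 35% | 49% | 27.0 |
| 29% | 69% | 83% | 19.4 |

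The n = 25 look falls at 25/2.33 = 10.7 months and the n = 30 look at 30/2.33 = 12.9 months. So only the n = 25 column counts as warning before the annual review.

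**Cases avoided.** At 29%: 19.4 × 0.29 = 5.6 expected cases, against 8.1 among the 28 enrolled at month 12 (2.5 fewer, 31%) or 35 × 0.29 = 10.2 at full enrolment. At 21%: 27.0 × 0.21 = 5.7 against 5.9 at month 12, which is almost no difference, or against 35 × 0.21 = 7.4 at full enrolment.

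**The case against.** Oversight is far from absent. The medical monitor reviews each SAE within 48 hours and can request full DSMC review; the committee may ask for a cumulative SAE review (8.8). SAEs go to the next monthly DSMC meeting, and medical monitoring includes regular assessment of their number and type (9). The DSMC reviews cumulative toxicities for unexpectedly high frequency and can add ad hoc reviews (9.1.1). IPS is graded 1 to 5 (8.4.1), and the investigator reviews adverse events monthly (12). Annual review is a minimum, and the DSMC charter is not among the documents.

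All of this stands. A reader might infer that nobody would see IPS cases before month 12; the documents do not support that. What remains is narrower: none of these routes states an expected IPS frequency or a count that obliges review. A search for unexpected frequency has no stated expectation, and ad hoc reviews have no stated trigger. Non-serious IPS need not enter the SAE route, and the visit with specific attention to non-infectious pneumonia comes only at 100 to 150 days (7.3.2.2).

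Three other stronger readings also fail:

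- **That the protocol calls IPS its main risk.** Section 2.4.1 presents it as one potential risk, listed first, ahead of relapse, delivery error and unknown risks.
- **That 29% is the rate to expect, with about 8 cases and, at the cited 45% mortality, 28 × 0.29 × 0.45 = 3.7 deaths before review.** That series used opposed lateral beams without lung shielding, whereas this trial aims for a mean lung dose below 9 Gy. The 45% describes all IPS cases in the series, not the high-dose-rate group. Section 2.4.3 also reports that the limited IMRT-technique data show no link between dose rate and pneumonitis. 29% is an adverse scenario within a 7% to 35% range.
- **That a count rule would prevent most of the excess.** The case counts above show a modest gain at 29% and almost none by month 12 at 21%.

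**Conclusion.** The point holds as a gap in the plan, and it should be fixed. Section 9.1.1 relies on interim time points that are specified nowhere, and the key secondary safety endpoint has no prespecified cumulative trigger. This finding rests on the text alone.

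The timing depends on accrual: 28 of 35 enrolled at the first mandatory review if accrual is uniform over 15 months, 17.5 if it takes 24 months, and fewer if the DSMC chooses to meet earlier. The gain from an explicit boundary is real but moderate. The example rule's figures treat IPS as known when it occurs. The definition requires excluding infection and cardiac, renal and fluid causes, and about 2.33 × 3.29 = 7.7 more subjects enrol in any 100 days, so the figures are somewhat optimistic. The early median onset limits that bias but does not remove it.

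**What to change.** In sections 9.1.1 and 10.1, name the interim time points, for example after every 5 treated subjects, and have the cumulative IPS count and number treated sent to the existing DSMC at each. Prespecify a boundary for study-level review, state whether accrual is held while the review takes place, and say how subjects still within the 100-day window are counted. Report the operating characteristics over the protocol's own range of rates.

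The Beta(0.2, 1.8) rule with a 0.97 cut-off (3/5, 4/10, 5/15, 6/20, 7/25, 7/30) is one worked example. The look spacing, prior and cut-off are choices to be justified, and the clinical team should set the acceptable IPS rate. The boundary concerns review of the study, not the care of individual subjects.

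The cost is protocol and SAP wording, a short tabulation per 5 subjects, and, with the example rule, about a 4% chance of an unneeded pause if the true rate is 10%.
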